## **15.4 Appendix 4: iRANO (immunotherapy response assessment in neuro-oncology) Criteria**

Tumor response will be assessed every 8 weeks for patients treated on this study using RANO criteria, however non-traditional iRANO criteria may be considered for patient management as outlined in the **Study Procedures (Section 6)**.

### **Anti-Tumor Effect Definitions**

Evaluable for objective response. Only those participants who have measurable disease present at baseline (obtained within 14 days of cycle 1, day 1) scan and have received at least one dose of therapy will be considered evaluable for response. These participants will have their response classified according to the definitions stated below. (Note: Participants who exhibit objective disease progression or die prior to the end of cycle 1 will also be considered evaluable.)

Measurable disease. Bi-dimensionally, contrast-enhancing, measurable lesions with clearly defined margins by CT or MRI scan, with a minimal diameter of 1 cm, and visible on 2 axial slices which are at least 5 mm apart with 0 mm skip. Measurement of tumor around a cyst or surgical cavity, if necessary, requires a minimum thickness of 3 mm. If there are too many measurable lesions to measure at each evaluation, the investigator must choose the largest two to be followed before a participant is entered on study. The remaining lesions will be considered non-measurable for the purpose of objective response determination. Unless progression is observed, objective response can only be determined when all measurable and non-measurable lesions are assessed.

Non-measurable evaluable disease. Unidimensionally measurable lesions, masses with margins not clearly defined, lesions with maximal diameter < 1cm.

### **Response/Progression Categories**

Complete response (CR). All of the following criteria must be met:

1. Complete disappearance of all enhancing measurable and non-measurable disease sustained for at least 4 weeks. In the absence of a confirming scan 4 weeks later, this scan will be considered only stable disease.
2. No new lesions\*.
3. All measurable and non-measurable lesions must be assessed using the same techniques as baseline.
4. Participants must be on no steroids or must not be on increased doses of steroids within 2 weeks of assessment relative to the dose taken at the time of the previous assessment
5. Stable or improved non-enhancing (T2/FLAIR) lesions
6. Stable or improved clinically, for clinical signs and symptoms present at baseline and recorded to be disease related

*Participants with non-measurable disease cannot have a complete response. The best response possible is stable disease.*

*\*See immunotherapy considerations below regarding new lesions*

Partial response (PR). All of the following criteria must be met:

1. Greater than or equal to 50% decrease compared to baseline in the sum of products of perpendicular diameters of all measurable enhancing lesions sustained for at least 4 weeks. In the absence of a confirming scan 4 weeks later, this scan will be considered only stable disease.
2. No progression of non-measurable disease.
3. No new lesions.\*

CONFIDENTIAL

This material is the property of the NYU School of Medicine. Do not disclose or use except as authorized in writing by the study sponsor

4. All measurable and non-measurable lesions must be assessed using the same techniques as baseline.
5. Participants must be on no steroids or must not be on increased doses of steroids within 2 weeks of assessment relative to the dose taken at the time of the previous assessment
6. Stable or improved non-enhancing (T2/FLAIR) lesions on same or lower dose of corticosteroids compared to baseline scan.
7. Stable or improved, for clinical signs and symptoms present at baseline and recorded to be disease related clinically.

*Participants with non-measurable disease cannot have a partial response. The best response possible is stable disease.*

*\*See immunotherapy considerations below regarding new lesions*

Progressive disease (PD). Any of the following criterion must be met:

1. 25% increase in sum of the products of perpendicular diameters of enhancing lesions (over best response or baseline if no decrease) on stable or increasing doses of corticosteroids
2. Patients who decrease corticosteroid use within 2 weeks of MRI assessment relative to the dose taken at the time of the previous assessment cannot be classified as having progressive disease and should be classified as non-evaluable.
3. Any new enhancing measurable lesion\*
4. Clear clinical deterioration not attributable to other causes apart from the tumor (e.g. seizures, medication side effects, complications of therapy, cerebrovascular events, infection, etc.). The definition of clinical deterioration is left to the discretion of the investigator but it is recommended that a decline in the Karnofsky Performance Score (KPS) from 100 or 90 to 70 or less, a decline in KPS of at least 20 from 80 or less, or a decline in KPS from any baseline to 50 or less, for at least 7 days, be considered neurologic deterioration, unless attributable to co-morbid events or changes in corticosteroid dose.
5. Failure to return for evaluation due to death or deteriorating condition

*\*See immunotherapy considerations below regarding new lesions*

Stable disease (SD). All of the following criteria must be met:

1. Does not qualify for CR, PR, or progression.
2. All measurable and non-measurable sites must be assessed using the same techniques as baseline.
3. Stable clinically.

Unknown response status. Progressive disease has not been documented and one or more measurable or non-measurable lesions have not been assessed.

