### 6.6.2 Efficacy Assessment

**Local reading (investigator assessment)** will be used to determine eligibility and for participant management. Response Assessments will be performed on every brain imaging assessment performed on protocol per standard **RANO criteria**. However, due to the known for patient management, non-traditional iRANO criteria may be used.

- Refer to Appendix 3 for details on iRANO criteria, guidelines for assessing radiologic findings, and treatment algorithm for the assessment of progressive imaging findings in patients with neuro-oncological malignancies undergoing immunotherapy.

**Evaluable for objective response.** Only those participants who have measurable disease present at baseline (obtained within 14 days of Cycle 1, Day 1) scan and have received at least one dose of therapy will be considered evaluable for response. These participants will have their response classified according to the definitions stated in Appendix 3. (Note: Participants who exhibit objective disease progression or die prior to the end of cycle 1 will also be considered evaluable.)

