### 7.2.2 Main Study Cohort - Phase II trial design

A single-stage design will be utilized to estimate overall survival, with a hypothesized 1yr-OS of 60%= $H_1$  and 35%= $H_0$ . We will enroll 24 patients; this design has a two-sided Type I error of 0.05 and a power of 80%.

For endpoint analyses, one year will be defined as 48 weeks (8 cycles) and two years will be defined as 96 weeks (16 cycles). Patients will be evaluated for radiographic responses by conventional contrast enhanced MRI every 8 weeks. Radiographic response assessments will be determined using RANO criteria for GBM.

1yr-OS and radiographic response rates will be estimated with exact 95% confidence intervals; with 24 patients, a 95% CI will be no more than 0.4 units wide. OS will be determined from the time of treatment initiation until the time of death due to any cause, with OS being censored at last follow-up if the patient remained alive. Patients who were last known to be alive and progression-free will be censored at the latest disease assessment. The Kaplan–Meier curves will be used to summarize OS and to estimate the medians.

PFS is defined as the time between treatment initiation and first occurrence of disease progression or death, and will be censored at last follow-up if the patient remained alive without disease progression. PFS is defined as the time from the first dose of study treatment to the earlier of disease progression or death due to any cause. Patients who initiate alternate anticancer therapy in the absence of documented progression will be censored at the latest disease assessment prior to initiation of such therapy. Patients with no post-baseline disease assessments will be censored at the Cycle 1 Dose 1 date unless death occurred prior to the first planned assessment (in which case the death will be considered a PFS event). The Kaplan–Meier curves will be used to summarize PFS and to estimate the medians.

Overall response rate (ORR) is defined as the proportion of patients who achieve best overall response of complete or partial response at any time after initiation of study treatment (prior to initiation of alternate anticancer treatment). Duration of response is defined as the number of months from the time criteria are first met for either CR or PR, until the first date that PD is objectively documented. The duration of objective response will be summarized descriptively using the Kaplan-Meier method.

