#### Special Considerations for Immunotherapies.

Appearance of new lesions is a criterion that defines progression of disease by RANO criteria. However, transient appearance of new enhancing lesions at either local or distant sites might occur in patients with neuro-oncological malignancies receiving immunotherapy. In such situations, careful radiological and clinical assessments are warranted. In some cases, new enhancing lesions might represent immune responses directed against infiltrative brain tumor cells. In addition, Immune-related response criteria guidelines for non-brain tumor cancers state that early increases in lesion size or new lesions do not define progressive disease unless further progressive changes are confirmed upon follow-up imaging, provided that patients do not have a clinical decline. Therefore, confirmation to define progressive disease is an important, novel aspect of immune-related response criteria. Additionally, the converse argument, the need of follow-up imaging to confirm a radiographic response, has been an accepted component of most response assessment metrics including RANO.

CONFIDENTIAL

This material is the property of the NYU School of Medicine. Do not disclose or use except as authorized in writing by the study sponsor

Confirmation of radiographic progression to define progressive disease in iRANO:

- iRANO recommends confirmation of disease progression on follow-up imaging **3 months after initial radiographic progression** if there is no new or substantially worsened neurological deficits that are not due to comorbid events or concurrent medication, and it is 6 months or less from starting immunotherapy.
- Imaging within the 3-month follow-up can be done as medically appropriate at the discretion of the treating clinician.
- The appearance of new lesions 6 months or less from the initiation of immunotherapy alone does not define progressive disease.
- If follow-up imaging confirms disease progression, the date of actual progression should be back-dated to the date of initial radiographic progression.

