Note on continuation of therapy pending confirmation of radiographic disease progression: iRANO recommends confirmation of disease progression on **follow-up imaging 3 months after initial radiographic progression** if there is no new or substantially worsened neurological deficits that are not due to comorbid events or concurrent medication, and it is 6 months or less from starting immunotherapy (see **Appendix 3** for iRANO criteria details). A decision of whether a patient should continue immunotherapy pending confirmation of radiographic disease progression should be established based on perceived benefits and risks. Continuation of immunotherapy may be considered pending follow-up imaging as long as subjects are deriving apparent clinical benefit with minimal and acceptable toxic effects.

By contrast, investigators may consider interrupting immunotherapy for subjects who need a substantial increase in corticosteroids (i.e., >4 mg of dexamethasone or equivalent per day) for evolving symptoms associated with brain edema or who have more than mild treatment-related toxic effects such as at least grade 2 irAEs. These guidelines are included to limit the likelihood of progressive immunotherapy-induced inflammatory changes leading to substantial deficits in otherwise stable or symptom-free patients. In such subjects, an interruption of immunotherapy dosing might be considered pending follow-up imaging.

Furthermore, investigators may discontinue or interrupt immunotherapy at any time if this option seems to be in the best medical interest of the subjects. As a general guidance, resumption of immunotherapy might be taken into account when systemic dexamethasone is decreased to 4 mg/day or less and the contrast-enhancing tumor burden is classified as stable disease, partial response, or complete response on a follow-up scan, or when relevant treatment-related toxic effects have resolved to grade 1 or less or pre-treatment baseline.

The iRANO Response Criteria to be used in this study are summarized in the Table below.

CONFIDENTIAL

This material is the property of the NYU School of Medicine. Do not disclose or use except as authorized in writing by the study sponsor

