## Summary of iRANO Response Criteria

Complete response	Disappearance of all enhancing disease for $\geq 4$ weeks; no new lesions; stable or improved T2/FLAIR; no more than physiological steroids; clinically stable or improved
Partial response	$\geq 50\%$ decrease in the sum of biperpendicular diameters of enhancing disease for $\geq 4$ weeks; no new lesions; stable or improved T2/FLAIR; stable or decreased steroid dose; clinically stable or improved
Minor response	NA
Stable disease	Does not qualify for complete response, partial response, or progressive disease; no new lesions; stable or improved T2/FLAIR; stable or decreased steroid dose; clinically stable or improved
Progressive disease	$\geq 25\%$ decrease in the sum of biperpendicular diameters of enhancing disease; or new lesions; or substantial worsened T2/FLAIR; or substantial clinical decline

[figure not shown]
**Note:** iRANO recommends confirmation of disease progression on follow-up imaging 3 months after initial radiographic progression if there is no new or substantially worsened neurological deficits that are not due to comorbid events or concurrent medication, and it is 6 months or less from starting immunotherapy. If follow-up imaging confirms disease progression, the date of actual progression should be back-dated to the date of initial radiographic progression. The appearance of new lesions 6 months or less from the initiation of immunotherapy alone does not define progressive disease. FLAIR=fluid-attenuated inversion recovery.

**Note:** Typographical error in the Progressive Disease definition, the correct criteria should be "increase" rather than "decrease".

CONFIDENTIAL

This material is the property of the NYU School of Medicine. Do not disclose or use except as authorized in writing by the study sponsor

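### The response appendix holds two rule sets that disagree on progression and stable disease, so one scan can give two PFS outcomes and the stated RANO/iRANO split is not carried through

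*Combined protocol and SAP*

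**What the plan says.** **Which criteria apply.** Section 7.2.2 states: "Radiographic response assessments will be determined using RANO criteria for GBM". Section 6.6.2 also names RANO and allows iRANO for patient management, but then adds: "These participants will have their response classified according to the definitions stated in Appendix 3". The appendix (15.4) opens with the same split, then classifies evaluable participants by its own definitions, and later says: "The iRANO Response Criteria to be used in this study are summarized in the Table below".

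**The numbered list** (Response/Progression Categories). Progression by size is "25% increase in sum of the products of perpendicular diameters of enhancing lesions (over best response or baseline if no decrease", on stable or increasing corticosteroids. Other items are a new lesion that is enhancing and measurable, clinical deterioration, and failure to return because of death or decline. A patient whose steroids were cut within 2 weeks of the scan is non-evaluable and cannot be called progressed. Stable disease is whatever remains, given the same technique and clinical stability. For complete response: "Participants must be on no steroids or must not be on increased doses of steroids within 2 weeks of assessment", compared with the previous assessment.

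**The summary table.** After the size criterion, progression includes "or new lesions; or substantial worsened T2/FLAIR; or substantial clinical decline". Stable disease also requires no new lesion, T2/FLAIR no worse and steroids no higher. Complete response requires "no more than physiological steroids; clinically stable or improved".

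**The new-lesion exception.** The list's new-lesion item carries an asterisk to the immunotherapy note, which says: "The appearance of new lesions 6 months or less from the initiation of immunotherapy alone does not define progressive disease". The same note states that under RANO a new lesion does define progression.

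**The concern.** Two people who follow the plan faithfully can code the same scan differently, one from the list and one from the table. Section 7.2.2 defines PFS by progression or death but does not say what progression is, so the appendix has to supply it. PFS and duration of response are secondary endpoints in both cohorts of an open-label trial without a control arm. If the rule is not fixed beforehand, it can be chosen once the scans are known. The correlative-studies appendix also uses PFS6 as an outcome for several tumor-tissue analyses, and that milestone falls where the new-lesion rule changes.

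**Working it through.** The plan gives no figure to reproduce here. The check sets the two rule sets side by side.

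**Step 1: where the definitions are.** No RANO definition appears outside the appendix. Reference 90, cited for RANO in 3.1.3, 6.6.2 and 7.2.2, is a paper on an MHC-binding prediction tool. A RANO paper is in the list as item 85 and again under a second number 91. Section 6.6.2 points to Appendix 3. The contents page gives that number to iRANO, but the body gives it to the Karnofsky scale and heads iRANO as Appendix 4.

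**Step 2: the same scan under both.** Assumptions: clinically stable, any response confirmed at 4 weeks, and more than 6 months since starting immunotherapy, so that the early confirmation note does not apply. The table's printed 25% decrease is read as an increase, as its own note instructs.

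| Case | Numbered list | Summary table | Endpoint touched |
|---|---|---|---|
| a. Enhancement unchanged, T2/FLAIR substantially worse | Stable | Progression | PFS, duration of response |
| b. Enhancement unchanged, new lesion that is not enhancing and measurable | Stable | Progression | PFS, duration of response |
| c. 30% increase, steroids reduced | Non-evaluable | Progression | PFS, duration of response |
| d. Enhancement gone, steroids above physiological, unchanged and not above baseline | Complete response | Partial response | None for response rate |
| e. Enhancement gone, steroids raised within 2 weeks but still physiological | Stable | Complete response | Response rate |

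Case e could arise with replacement for adrenal insufficiency, which section 8.1 lists as an expected event.

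**Step 3: the first 6 months.** Here the table's footnote repeats the new-lesion exception, so the conflict is between the appendix and RANO as named in 7.2.2. A new enhancing measurable lesion alone is progression under RANO and not under the asterisked note. Scans are due every 8 weeks from study drug start. Those at weeks 8, 16 and 24 fall inside about 26 weeks, so three scheduled scans are exposed. If progression is later confirmed, the note back-dates it to the first scan and the PFS date agrees. The results differ when it is never confirmed, for example if the lesion resolves or the patient dies first.

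**Step 4: response rate.** Only complete and partial responses count, so cases a to c do not turn a responder into a non-responder at that scan. Case d stays a responder under both. Case e does not, whichever comparator is used for the table's steroid condition, which names none. One patient is 1/24 = 4.2 percentage points in the main cohort and 1/16 = 6.25 points in the surgical cohort. The step is larger if only patients with measurable baseline disease are counted.

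**The case against.** The strongest reply is that the hierarchy is stated many times. The synopsis, 3.1.3, 6.1, 6.6.2, the footnotes to both schedules of events and the opening of the appendix all name RANO for assessment and iRANO for management. Section 7.2.2 names RANO alone. The pointer in 6.6.2 concerns patients evaluable for objective response and does not mention PFS. The partial-response rules largely agree.

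All of that stands, and it shows what was intended. It does not settle how a scan is coded. The text that should contain the RANO rules is the list, whose new-lesion items are asterisked to the iRANO exception. The table is introduced as the study's criteria without a management-only limit. The citation that should lead to RANO leads elsewhere.

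The back-dating rule is a second fair reply. It removes the date difference for new-lesion progression that is later confirmed. It does nothing for cases a to c, where the list does not recognize progression on that scan at all.

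**Conclusion.** The inconsistency is real, and following the plan as written gives two PFS outcomes for the same scan. It reaches PFS and duration of response in both cohorts, and response rate only in narrow steroid cases such as e. The main cohort's primary endpoint, 1-year OS, and its sample size are unaffected. The conclusion rests on the wording of the list and the table and on the assumptions in step 2.

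A reader might infer more than the documents support:

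- **That a switch between stable disease and progression changes the response rate.** Both are non-responses.
- **That the complete-response steroid conflict generally changes it.** In case d the patient is a responder either way.
- **That a number of affected patients can be given.** Nothing states how often progression rests on T2/FLAIR or a new lesion alone.
- **That a single local reader decides the endpoint.** Section 6.6.2 gives local reading for eligibility and management and names no endpoint reader.
- **That a comparison with historical PFS is compromised.** Section 7.2.2 plans Kaplan-Meier estimation of PFS, with no such comparison.

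**What to change.** 1. State in 7.2.2 and 6.6.2 that PFS, response rate and duration of response all use one rule set: RANO, as 7.2.2 already says.
2. Write that rule set out once in the appendix, with its T2/FLAIR, new-lesion, steroid and confirmation rules taken from the RANO publication. The documents alone do not show what RANO says on T2/FLAIR or steroids, so the iRANO table should not be used to fill those gaps.
3. Remove the asterisks to the iRANO note from the endpoint list.
4. Label the iRANO table and its 3-month confirmation and back-dating rule as patient management only, and reword the sentence that introduces the table.
5. Pre-specify iRANO-confirmed PFS as a sensitivity analysis on the same scans.
6. Make the appendix number agree between 6.6.2, the contents page and the body, and replace reference 90 where RANO is cited.

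The cost is wording in two sections and one appendix, plus one extra PFS analysis. No added imaging is needed. The change should be made before scans are classified for the endpoints.
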